Appendix 5. Eastern Cooperative Oncology Group (ECOG) Performance Status

Grade	ECOG
0	Fully active, able to carry on all pre-disease performance without restriction
1	Restricted in physically strenuous activity but ambulatory and able to carry out work of a light or sedentary nature, eg., light house work, office work
2	Ambulatory and capable of all self-care but unable to carry out any work activities. Up and about more than 50% of waking hours
3	Capable of only limited self-care, confined to bed or chair more than 50% of waking hours
4	Completely disabled. Cannot carry on any self-care. Totally confined to bed or chair
5	Dead

Appendix 6. Modified IWCLL 2008 Response Criteria

The determination of CLL response and progression will be based on standardized International Workshop on CLL (IWCLL) 2008 criteria {Hallek 2008}, as specifically modified for this study to reflect current recommendations which consider the mechanism of action of small molecule targeted therapy {Cheson 2012}.

Complete remission (CR):

All below listed criteria must be fulfilled and no disease related symptoms should be present.

Complete remission with incomplete recovery of the bone marrow (CRi):

All below listed criteria must be fulfilled, except for an incomplete recovery of the bone marrow with persisting anemia, thrombocytopenia and/or neutropenia (related to toxicity of treatment and not due to CLL) and no disease related symptoms should be present.

Partial response (PR):

Among the below listed criteria at least 2 from group A and 1 from group B must be fulfilled.

Partial response with lymphocytosis (PR-L):

Among the below listed criteria at least 2 from group A and 1 from group B must be fulfilled, however, a lymphocytosis related to treatment may be present.

Nodular partial response (nPR):

All criteria for a CR/CRi are fulfilled, but the bone marrow shows lymphoid nodules. As in a lot of cases these nodules are related to bone marrow proliferation during recovery, efforts should be made to prove that these lymphocytes are no CLL cells by 4-colour-flow cytometry to be able to define these patients as CR/CRi. If this cannot be proved by either FACS or MRD from the bone marrow patients will be considered PR and therefore this category will not appear on the eCRF.

Stable disease (SD):

Failure to achieve a PR and absence of PD.

Progressive disease (PD):

Presence of at least 1 of the below enlisted criteria or appearance of new lymph nodes > 1.5 cm, hepato- or splenomegaly or organ infiltration by CLL.

Response criteria

Parameter	CR	CRi	PR	PR-L	PD
Group A (indicating tumor load)					
Lymphadenopathy ¹	none > 1.5 cm		decrease \geq 50%		increase by \geq 50% or new lymph nodes \geq 1.5 cm
Hepatomegaly	none		decrease \geq 50%		Increase by \geq 50 %
Splenomegaly	none		decrease \geq 50%		Increase by \geq 50 %
Blood lymphocytes	< 4000/ μ L		decrease of \geq 50% from baseline	increase	Increase by \geq 50% over baseline ² to \geq 5000/ μ L
Bone marrow	Normocellular	hypocellular	50% reduction in BM infiltrates ³		irrelevant
	30% lymphocytes, no B-lymphoid nodules				
Group B (indicating function of the hematopoietic system)					
Platelet count	\geq 100000/ μ L	Irrelevant	\geq 100000/ μ L or increase by \geq 50% from baseline		Decrease by \geq 50% due to CLL
Hemoglobin	> 11 g/dL	irrelevant	> 11 g/dL or increase by \geq 50% from baseline		Decrease by > 2 g/dL
Neutrophil count	> 1500/ μ L	Irrelevant	> 1500/ μ L or increase by \geq 50% from baseline		irrelevant

- a Assessed as sum of the products of multiple lymph nodes, if available an indicator lymph node (the largest palpable) from every region should be compared in every staging.
- b Patients with treatment related lymphocytosis should not be rated PD and remain on study treatment if other criteria for progressive disease are absent.
- c In case of B lymphoid nodules a 4 colour flow cytometry is recommended to clarify if this is related to CLL, if FACS is negative these patients can be rated as CR/CRi, if all other criteria are fulfilled.

MRD response rate

The MRD response is assessed with four-color-flow cytometry (FACS) and MRD negativity is defined as one CLL cell per 10,000 leukocytes [0.01 %], ie, $<10^4$ and patients are defined as MRD negative if their disease burden is below this threshold MRD in the bone marrow will be assessed after the completion of 24 weeks of treatment and MRD in the peripheral blood will be assessed in the schedule outlined in [Appendix 2](#) in the event that peripheral blood ALC $<$ 4K/ μ L.

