3.5. Duration of Study

This study will continue to monitor subjects for up to 30 days post end of treatment, or up to Week 25 should a subject discontinue treatment prior to Week 25 for reasons other than disease progression.

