6.6.1. Hemorrhage

Bleeding events have occurred in subjects with relapsed/refractory chronic lymphocytic leukemia (CLL) and relapsed/refractory non-Hodgkin's lymphoma (NHL) who received tirabrutinib as monotherapy. These include minor hemorrhagic events such as contusion, hematoma, and petechiae, and major hemorrhagic events such as small intestinal hemorrhage and subdural hematoma.

Consider interrupting treatment with tirabrutinib for up to 7 days prior to surgery or other interventions associated with a significant risk of bleeding and resuming treatment once hemostasis is achieved.

Subjects should be monitored for signs of bleeding and treated appropriately.

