6.6.5. Hematological Events

In the Phase 1 experience with idelalisib in patients with NHL and CLL, subjects with Grade ≥ 3 neutropenia, anemia, and/or thrombocytopenia were enrolled to clinical trials. Decreased levels of neutrophil counts, hemoglobin, or platelet counts during idelalisib administration were largely due to minor fluctuations in these parameters among subjects with pre-existing hematological abnormalities due to disease or prior therapy. Thus, idelalisib did not appear to induce overt myelosuppression. Obvious patterns of drug-mediated reductions in circulating CD4+ lymphocyte counts or suppression of serum IgG levels were also not observed. Treatment-emergent Grade 3 or 4 neutropenia events including those accompanied by fever or infection have occurred in subjects treated with idelalisib, most commonly in the context of myelosuppressive agents such as bendamustine. All subjects will have their absolute neutrophil count monitored at least every two weeks for the first 24 weeks of idelalisib treatment.

Neutropenia and anemia have also occurred in subjects treated with tirabrutinib. The anemia in subjects treated with tirabrutinib has generally been self-limiting, without the requirement for intervention and with improvement on continued therapy.

Management of neutropenia, including administration of G-CSF should be per established clinical guidelines and institutional standard of care.

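### The hemoglobin criterion for progression does not require the fall to be due to CLL and names no reference value, so one toxicity-related fall can fit CR or CRi and also PD, with no rule on which prevails

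*Protocol*

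**What the plan says.** Protocol Appendix 6 sets out the modified IWCLL 2008 criteria used for the primary endpoint and for ORR. Four parts of it bear on this point.

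- **Combination rule.** PD requires "Presence of at least 1 of the below enlisted criteria", or certain new findings in nodes, liver, spleen or other organs.
- **Blood counts in the PD column.** Hemoglobin: "Decrease by > 2 g/dL". Platelets: a fall of at least 50%, limited to falls due to CLL. Neutrophils: irrelevant. Lymphocytes: a rise of at least 50% over baseline to at least 5000/µL.
- **Lymphocytosis footnote (b).** "Patients with treatment related lymphocytosis should not be rated PD and remain on study treatment if other criteria for progressive disease are absent".
- **CRi.** Persisting cytopenia, including anemia, is accepted when it is "related to toxicity of treatment and not due to CLL", and the CRi column marks hemoglobin as irrelevant. The CR column requires hemoglobin above 11 g/dL.

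SAP 6.1.1 counts CRi as CR for the primary endpoint. SAP 6.2 refers back to the modified criteria for each response category. Neither adds a rule on the cause of a hemoglobin fall.

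The protocol foresees falls that are not due to CLL. Section 6.6.5 states: "Neutropenia and anemia have also occurred in subjects treated with tirabrutinib". Section 6.6.1 reports bleeding with tirabrutinib, including "major hemorrhagic events such as small intestinal hemorrhage and subdural hematoma". Response is investigator-assessed (Protocol 8.5.1), without an adjudication committee (8.11).

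**The concern.** Of the three blood counts that can trigger PD, hemoglobin is the only one with no protection against a drug effect. The explicit qualifier on platelets, directly above, invites a literal reader to conclude that the cause of a hemoglobin fall does not matter.

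The same appendix treats toxicity-related anemia as compatible with CRi. Two investigators who apply the table faithfully to one subject could therefore record opposite categories, one a success on the primary endpoint and the other PD. With about 30 subjects in Arm B, a few such calls would move the CR rate and ORR visibly.

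**Working it through.** The plan gives no figure for this point, so the check is mainly one of logic.

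**1. Can one fall meet both a response category and PD?** The hemoglobin values below are illustrative assumptions. PD as written means that start minus later value exceeds 2 g/dL.

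| Hemoglobin (g/dL) | Fall | CR entry (> 11) | CRi entry | PD entry |
|---|---|---|---|---|
| 14.0 to 11.5 | 2.5 | met | irrelevant | met |
| 12.0 to 9.5, from toxicity | 2.5 | not met | irrelevant | met |
| 13.0 to 11.0 | 2.0 | not met | irrelevant | not met |

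If all other requirements for response are fulfilled, the first subject fits CR and PD, and the second fits CRi and PD. PR overlaps as well. It needs two Group A criteria and only one from Group B, and hemoglobin of 11.5 g/dL supplies that one. This is how ORR is affected.

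**2. Does any rule settle the overlap?** In Appendix 6 only stable disease is defined as requiring the absence of PD. The definitions of CR, CRi, PR and PR-L do not say so, and none states that it overrides PD. The lymphocytosis exemption also depends on no other PD criterion being present, so a drug-related hemoglobin fall can cancel it.

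**3. Fall from what?** The lymphocyte entry names baseline. The hemoglobin entry names nothing, and the platelet entry is silent too. Take baseline 10.0, best value 12.0 and a later value of 9.5 g/dL. From baseline the fall is 10.0 − 9.5 = 0.5, which is not PD. From the best value it is 12.0 − 9.5 = 2.5, which is PD.

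**4. Scale per subject.** The inputs are n = 30 in Arm B (Protocol 8.9) and the planned two-sided 90% Clopper-Pearson interval (Protocol 8.5.1). For x responders, the lower limit is the 0.05 quantile of Beta(x, n − x + 1) and the upper limit is the 0.95 quantile of Beta(x + 1, n − x). At x = 9 this reproduces the 30% row of Table 8-1.

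| Responders rated PD on hemoglobin | CR rate | 90% CI |
|---|---|---|
| 0 | 9/30 = 30.0% | 16.6% to 46.5% |
| 1 | 8/30 = 26.7% | 14.0% to 43.0% |
| 2 | 7/30 = 23.3% | 11.5% to 39.4% |

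Each such subject costs 1/30 = 3.3 points, about one fifth of the ±17.0 points that the plan gives as its precision (3.3/17.0 = 0.19).

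**The case against.** The strongest defense is that investigators will use judgment and that the chain from a hemoglobin fall to a lost responder has several breaks. Most of this stands as a limit on the consequences.

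- **Treatment does not stop automatically.** A reader might infer that a hemoglobin-only PD ends treatment. Protocol 3.3 continues the oral drugs in the absence of progression, but 3.4 is permissive, and the reason it lists is progression of CLL, which itself implies attribution.
- **Interim visits do not record formal PD.** Under SAP 6.4 the worst category of the clinical assessment is suspected progressive disease, and Protocol 6.2.11 allows extra scans when progression is suspected.
- **The Week 25 scan is not clearly lost.** Protocol 3.5 extends monitoring to Week 25 for subjects who stop early "for reasons other than disease progression", and 6.7 is similar. The scan rule in 6.2.11 refers to disease progression in general but names only radiographic progression, or the start of other CLL therapy, as an exception. The text is ambiguous.
- **Non-response does not follow automatically.** The visible SAP rule is triggered by other anti-cancer therapy, and Protocol 8.3 by missing assessments. Week 25 status comes from the record closest to the nominal day (SAP 3.8.3). A fall that has recovered by then costs nothing if the assessment is made, and Protocol 6.6.5 describes tirabrutinib anemia as generally self-limiting.
- **The CRi definition already addresses toxicity-related anemia.** It does, but it creates the overlap with PD and does not resolve it.

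A reader might also take the 25% anemia rate with idelalisib plus obinutuzumab (Protocol 1.4) and project 0.25 × 30 = 7.5 affected subjects. The documents do not support this. The rate comes from 32 previously untreated subjects at a higher idelalisib dose. It counts adverse events of any grade, not falls above 2 g/dL from causes other than CLL. In the doublet study, anemia is not among the events listed for more than 10% of 23 subjects (Protocol 1.3.4).

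Judgment does not remove the defect itself. No visible text tells investigators to exclude other causes for hemoglobin, and no adjudication would harmonize their calls.

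**Conclusion.** The point holds as an internal conflict in the response criteria. One toxicity- or bleeding-related hemoglobin fall of more than 2 g/dL can satisfy both a response category and PD, the reference value is not stated, and nothing visible decides which category prevails. CR/CRi and ORR at Week 25 can be misclassified as a result.

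The total effect cannot be estimated, because the documents give no frequency of such falls. The cost is 3.3 points for each Arm B subject who would otherwise respond and is rated PD on this ground, and nothing for subjects who would not have responded. The analysis is descriptive, so no test result is at stake.

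Two assumptions remain. Part of SAP section 6 is redacted, so an attribution rule there cannot be excluded. The guideline behind Appendix 6 was not available, and the study-specific table is taken as the operative text.

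**What to change.** 1. In Appendix 6, reconcile the hemoglobin PD entry with the platelet entry, the lymphocytosis footnote and the CRi definition, so that attribution is handled consistently for response classification. State the reference value for the fall; the platelet entry needs one too.
2. State which category prevails when a subject meets CR or CRi (or PR) and also PD on hemoglobin alone.
3. Repeat both rules in SAP 6.1.1 and 6.2.
4. List every PD that rests on hemoglobin alone, with the recorded cause and the Week 25 category, so that any effect on CR and ORR can be seen.

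Protocol 3.3 and 3.4 tie progression to stopping treatment. The sponsor should check them against the reconciled wording. No stopping rule is proposed here.

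The cost is small: one or two table cells, one precedence sentence, eCRF guidance and one listing. If data collection is already complete, items 3 and 4 can still be done from recorded data. SAP section 1 already requires changes made after SAP finalization to be documented in the CSR.

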Appendix 7. Cumulative Illness Rating Scale (CIRS)

The CIRS used in this protocol is designed to provide an assessment of recurrent or ongoing chronic comorbid conditions. For each condition selected from the CIRS List of Comorbid Conditions, please rate the severity of that condition. For the severity rating, please use the scoring guidelines shown in the table below, considering the magnitude of symptoms, how manageable the condition is, and the extent of intervention required.

Please take into account that CLL induced illness or organ damage are not included in this rating scale. The goal of this rating scale is to assess comorbidity other than CLL in the patient. If there are two or more illnesses/impairments of one organ system, the illness/impairment with the highest severity should be evaluated.

CIRS Rating Strategy of Comorbidity

Score	Severity	Findings
0	No problem	Organ system not compromised
1	Mild	Illness/impairment with/without requirement of therapy, excellent prognosis, patient with normal activity
2	Moderate	Illness/impairment requiring therapy, good prognosis, compromised activity of patient
3	Severe	Illness/impairment with urgent requirement of therapy, prognosis unclear, marked restriction in activity
4	Extremely severe	Life threatening illness/impairment, emergency case of therapy, adverse prognosis

CIRS List of Comorbid Conditions

Organ System	If illness/impairment present, please specify	Score ¹
Heart		
Blood Pressure		
Vascular		
Respiratory		
Eye/ear/nose/throat/larynx		
Upper gastrointestinal		
Lower gastrointestinal		
Liver		
Renal		
Genitourinary		
Musculoskeletal		
Endocrine/metabolic		
Neurological		
Psychiatric		
Total Score		

Appendix 8. Cockcroft-Gault Method for Estimating Creatinine Clearance

Formulas for calculating the estimated creatinine clearance (eC_{cr}) are provided in the table below. The formula appropriate to the units in which serum creatinine was measured and the subject's gender should be used.

Serum Creatinine Units	Gender	Formula
mg/dL	Males	$eC_{cr} \text{ [mL/min]} = \frac{(140 - \text{subject age [years]}) \times \text{subject weight [kilograms]} \times 1}{72 \times \text{subject serum creatinine [mg/dL]}}$
	Females	$eC_{cr} \text{ [mL/min]} = \frac{(140 - \text{subject age [years]}) \times \text{subject weight [kilograms]} \times 0.85}{72 \times \text{subject serum creatinine [mg/dL]}}$
μmol/dL	Males	$eC_{cr} \text{ [mL/min]} = \frac{(140 - \text{subject age [years]}) \times \text{subject weight [kilograms]} \times 1.23}{\text{Subject serum creatinine [μmol /L]}}$
	Females	$eC_{cr} \text{ [mL/min]} = \frac{(140 - \text{subject age [years]}) \times \text{subject weight [kilograms]} \times 1.04}{\text{Subject serum creatinine [μmol /L]}}$

Abbreviation: eC_{cr} estimated creatinine clearance

Appendix 9. Binet and Rai Staging Systems for the Classification of CLL

Binet

Stage	Lymph Node Areas	Hemoglobin < 10 g/dL	Platelet < 100 × 10 ⁹ /L
A	< 3	No	No
B	≥ 3	No	No
C	±	Either present	

Rai

Stage	Lymphocytosis	Lymph Node Enlargement	Spleen/Liver Enlargement	Hemoglobin < 11 g/dL	Platelet < 100 × 10 ⁹ /L
0	Yes	No	No	No	No
I	Yes	Yes	No	No	No
II	Yes	±	Yes	No	No
III	Yes	±	±	Yes	No
IV	Yes	±	±	±	Yes

Appendix 10. The G8 Screening Questionnaire

- 8 questions
- Nurse administered
- Takes 5-10 minutes to perform
 - Appetite, weight loss, BMI
 - Mobility
 - Mood and cognition
 - Number of medications
 - Patient related health
 - Age categories
- Abnormal if score ≤ 14
 - Preliminary analysis
 - Sensitivity: 89.6%
 - Specificity: 60.4%

	Items	Possible answers (score)
A	Has food intake declined over the past 3 months due to loss of appetite, digestive problems, or chewing or swallowing difficulties?	0: severe decrease in food intake
		1: moderate decrease in food intake
		2: no decrease in food intake
B	Weight loss during the last 3 months	0: weight loss > 3 kg
		1: does not know
		2: weight loss between 1 and 3 kg
		3: no weight loss
C	Mobility	0: bed or chair bound
		1: able to get out of bed/chair but does not go out
		2: goes out
E	Neuropsychological problems	0: severe dementia or depression
		1: mild dementia or depression
		2: no psychological problems
F	Body mass index (BMI weight in kg) / (height in m) ²	0: BMI < 18.5
		1: BMI = 18.5 to BMI < 21
		2: BMI = 21 to BMI < 23
		3: BMI = 23 and > 23
H	Takes more than 3 prescription drugs per day	0: yes
		1: no
P	In comparison with other people of the same age, how do they consider their health status?	0: not as good
		0.5: does not know
		1: as good
		2: better
	Age	0: > 85 yr
		1: 80 85 yr
		2: < 80 yr
	Total Score	0-17

MedDRA	Medical Dictionary for Regulatory Activities
NLP	Natural Language Processing
nPR	nodular partial response
ORR	overall response rate
CCI	
PB	peripheral blood
PD	progressive disease
CCI	
PP	per protocol

PR	partial response
PR-L	partial response with lymphocytosis
PT	preferred term
Q1, Q3	first quartile, third quartile
QRS	electrocardiographic deflection between the beginning of the Q wave and termination of the S wave representing time for ventricular depolarization
QT	electrocardiographic interval between the beginning of the Q wave and termination of the T wave representing the time for both ventricular depolarization and repolarization to occur
QTc	QT interval corrected for heart rate
QTcF	QT interval corrected for heart rate using Fridericia's formula
RR	electrocardiographic interval representing the time measurement between the R wave of one heartbeat and the R wave of the preceding heartbeat
SAP	statistical analysis plan
SD	stable disease
StD	standard deviation
SI (units)	international system of units
SOC	system organ class
TEAE	treatment-emergent adverse event
TFLs	tables, figures, and listings
CCI	
ULN	upper limit of normal
VR	ventricular rate
WHO	World Health Organization

1. INTRODUCTION

This statistical analysis plan (SAP) describes the statistical analysis methods and data presentations to be used in tables, figures, and listings (TFLs) in the synoptic clinical study report (CSR) for Study GS-US-401-1958. This SAP is based on the study protocol amendment 6 dated 28 May 2020 and the electronic case report form (eCRF). The SAP will be finalized before database finalization. Any changes made after the finalization of the SAP will be documented in the CSR.

1.1. Study Objectives

The primary objective of this study is:

- To determine the preliminary efficacy of the combination of tirabrutinib and idelalisib with obinutuzumab in subjects with relapsed or refractory chronic lymphocytic leukemia (CLL)

The secondary objective of this study is:

- To evaluate the safety and tolerability of the combination of tirabrutinib and idelalisib with and without obinutuzumab

CCI

1.2. Study Design

This is a Phase 2, prospective, open-label, multicenter trial to evaluate the safety and efficacy of the combination of tirabrutinib and idelalisib with and without obinutuzumab in subjects with relapsed or refractory CLL.

Eligible subjects will be randomized in a 1:1 manner to one of the following two arms, stratified by the presence of 17p deletion/TP53 mutation (del17p/TP53mut) in CLL cells:

- Arm A: tirabrutinib + idelalisib
- Arm B: tirabrutinib + idelalisib + obinutuzumab

With Amendment 3, randomization was discontinued. All subsequent subjects will be enrolled into Arm B.

Duration of Treatment:

Tirabrutinib 80 mg and idelalisib 100 mg will be self-administered orally once daily. Dosing of both agents will begin on Week 1 Day 1 of the study and thereafter continue for up to 104 weeks in the absence of disease progression, unacceptable toxicity, or documentation of complete remission (CR) with bone marrow minimal residual disease (MRD) negativity (CR/BM MRD-). If CR/BM MRD- is documented on study, treatment will stop after the earlier of:

- i) an additional 3 months of therapy or
- ii) 104 weeks of total treatment.

Obinutuzumab will be administered as 8 intravenous infusions of 1000 mg each over 21 weeks. A test dose of 100 mg will be administered on Week 1 Day 1. If this dose is tolerated, the remainder of the full dose may be subsequently administered on Day 1. Alternatively, the remaining 900 mg will be administered on Day 2. Subsequent infusions will be administered on Week 2 Day 1, Week 3 Day 1, Week 5 Day 1 and then every 4 weeks through Week 21.

This study will continue to monitor subjects for up to 30 days post end of treatment, or up to Week 25 should a subject discontinue treatment prior to Week 25 for reasons other than disease progression.

Efficacy Assessment Schedule:

Tumor response assessment per modified International Workshop on CLL (IWCLL) 2008 criteria will be performed at the Week 25 visit, with evaluation of areas affected by CLL during the screening evaluation. During the treatment phase, additional response assessment per IWCLL 2008 criteria may be performed as clinically indicated.

Clinical response based on physical exam, laboratory parameters and presence of B-symptoms will be performed every 4 weeks until Week 33 Day 1 (except for Week 25) and then every 12 weeks starting Week 33 until Week 105 following the modified IWCLL 2008 criteria, with the exception of lymphadenopathy, hepatomegaly, splenomegaly, and bone marrow.

Bone marrow MRD will be assessed at Week 25. Additional bone marrow MRD may be assessed as clinically indicated. Peripheral blood MRD will be assessed on Day 1 of Weeks 1, 13, 25, 33, 45, 105, and End of Treatment (EOT). EOT collection is not needed for subjects who complete the Week 105 visit.

The Schedule of Assessments is located in [Appendix 1](#).

